## **3.3 *Outcome Measures***

### **3.3.1 *ALSFRS-R***

The ALSFRS-R will be determined at all video/telephone visits (Appendix D). ALSFRS-R is a quickly administered (five minute) ordinal rating scale (ratings 0-4) used to determine patients' assessments of their capability and independence in 12 functional activities. All 12 activities are relevant in ALS. Initial validity was established in ALS patients by documenting change in ALSFRS-R scores correlated with change in strength over time, and it was closely associated with quality of life measures and predicted survival (23). The test-retest reliability is greater than

0.88 for all 13 items. The ALSFRS-R declines linearly with time over a wide range during the course of ALS. Recent work has shown that the measure can be conducted over the phone (24), and it can even be reliably conducted and recorded online by patients themselves (25). The ALSFRS-R will be administered to participants over video/telephone by the study coordinator at Duke on their enrollment visit. During this visit, the coordinator will also teach participants how to complete this measure themselves and to use the EM interface to record it. Calls from the coordinator will be made at weeks 1, 2 and 3 to provide additional training. Starting at week 4, participants will be asked to fill out the ALSFRS-R test on their PLM profile once every 30 days.

### **3.3.2 Participant Subjective Treatment Evaluation**

At all PLM virtual visits, participants will be asked to evaluate the intervention. They will be asked to provide information on perceived effectiveness, side effects, adherence, burden, unexpected positive effects, and advice & tips regarding the treatment (Appendix C). They will also be asked to complete Thrive Questionnaires to assess their quality of life (Appendix E).

### **3.3.3 Microbiome Sequencing**

The microbiome of study participants will be analyzed in saliva and stool samples at enrollment, week 4 and month 6 visits. Participants will be sent collection kits with which they will collect saliva and fecal samples and send by mail to Duke University for further analysis at each timepoint. Research personnel will deidentify the samples of any personally identifiable information (PII) and subsequently submit them to the Duke Microbiome Core (<https://genome.duke.edu/cores-and-services/microbiome-shared-resource>) for sample processing and preparation for biospecimens for long term archiving at the Duke University BioBank. The Duke Microbiome Core will perform DNA extraction, sequencing library preparation, and 16S rRNA sequencing on the Illumina MiSeq platform. Data analysis of the deidentified microbiome sequencing data will be conducted in collaboration with the Duke University Microbiome Center (DMC). Data will be compared within subjects with ALS to assess possible changes over the length of the study and identify microbial correlates of disease progression. Fecal microbiome data at enrollment, week 4 and month 6 will also be compared to data from healthy control participants from the same household as participants with ALS.

In addition, our collaborator [name] at the Duke Department of Molecular Genetics and Microbiology, will perform metagenomic analysis of deidentified selected fecal samples from patients that positively respond to Theracurmin to achieve strain level identification of microbes positively and negatively associated with improved outcomes. His group will also culture selected anaerobes (eg. *Akkermansia muciniphila*) that have been linked to ALS severity for further genetic and phenotypic characterization.

### **3.3.4 Safety and Tolerability in Patients with ALS**

We will record adverse and serious adverse events throughout the study. The PI will determine whether these are related to treatment. Patients will also measure and record their side effects at Month 0-6 Internet Visits on their PLM profile (See Appendix C).

### **3.3.5 Enrollment Rate**

Enrollment rate will be calculated as the number of participants enrolled per month. A previous meta-analysis showed the mean ALS trial enrollment rate to be 2.2 participants per site per month (4). Our previous Lunasin trial had an enrollment rate of 9 participants per site per month (6).

### **3.3.6 Retention**

Retention will be assessed by looking at the dropout rate at 6 months (the percentage of surviving enrolled patients who complete the Month 6 Visit). A previous meta-analysis of traditional clinical trials showed the mean ALS participant dropout rate to be 22% at 12 months (5). Our previous virtual trial with Lunasin had a dropout rate of 16% at 12 months (6).

## **3.4 Study Schedule**

Following informed consent and screening, enrollment visit activities will commence and Therarcurmin treatment will be started. Treatment and all study activities will end at month 6. Participants will be required to make 4 video/telephone visits with the Duke study team (enrollment, weeks 1, 2, and 3). Participants will not be required to make any physical visits to Duke. At months 2-6, participants will make “Internet PLM visits” by measuring their own ALSFRS-R score and weight and height, and logging onto the PLM website to record it as well as perceived efficacy, perceived side effects, perceived compliance, changes in concomitant medications and Thrive questionnaires. Participants will be reminded to log into their PLM profile and record the above-mentioned data points via email and text reminders from PLM. The study coordinator will call/video participants at enrollment, weeks, 1, 2, 3 and for training and any time afterward when participants have not entered data for 2 weeks beyond expected entries. The call script for such communications can be found in Appendix I.

### **3.4.1 Screening/Enrollment/Baseline Video/Telephone Visits**

During the enrollment visit(s) (can be one or two visits depending on patient preference and tolerance), participants will be consented. Inclusion and Exclusion Criteria will be reviewed to ensure the participant qualifies. Participants will be taught to self-administer the ALSFRS-R (23). Participants will be taught to register for an account on the website PLM and taught to enter their ALSFRS-R, perceived efficacy, compliance, adverse events and concomitant medications. The participant will complete/enter their current ALSFRS-R and weight and height in PLM during this visit. The ALSFRS-R has previously been validated for similar online use by patients (25).

[figure not shown]
### **3.4.2 Week 1,2,3 Video/Telephone Visits**

During the Week 1, 2, and 3 video/telephone the study coordinator will confirm that participants are logging into the PLM site and entering data without difficulty. The coordinator will measure an ALSFRS-R by phone and compare it to the participant-generated score. Differences will be reconciled as part of the teaching process.

### 3.4.3 Week 4 and Month 2-6 Internet PLM Visits

During the Week 4 and Month 2-6 Internet PLM Visits, participants measure their own ALSFRS-R and weight and height and will log into the PLM site to record these as well as perceived efficacy, adverse events, concomitant medications and Thrive questionnaires. If participants have not entered data within 7 days of a visit, they will receive a reminder email and text from PLM (Appendix I). If they still have not entered data after another 7 days, they will receive a reminder call from the study coordinator.

### 3.4.4 Study Timeline Overview Figure for Primary Participants

### 3.4.5 Schedule of Events Table for Primary Participants

The [Table 1](#) shows the schedule of visits for the Primary Participants, i.e. the patients with ALS (R=research staff initiated task, P=primary participant initiated task):

**Table 1: Schedule of Events for Primary Participants**

	Enrollment*	Wk 1,2,3	Wk 4	Mos 2-5	Mo 6**
Inclusion and exclusion criteria review	R				
Consent	R				
Participant registers account on PLM	R				
Phone/video visits with participant to record ALSFRS-R and teach/troubleshoot as necessary	R	R			
		P	P	P	P
PLM virtual visits by participant to record ALSFRS-R, anthropometrics, treatment self-evaluation, Con Meds, and AE					
Long Thrive Evaluation	P		P		P
Short Thrive Evaluation		P		P	
Microbiome sample collections by participant at-home	P		P		P

\*intervention begins

\*\*intervention ends

### 3.4.6 Schedule of Events Table for Control Participants

The **Table 2** shows the schedule of video/telephone visits for the Control Participants (R=research staff initiated task, C=control participant initiated task):

**Table 2: Schedule of Events for Control Participants**

	Screening/Enrollment	Wk 4 and Month 6
Consent	R	
Inclusion and Exclusion Criteria Review	R	
Microbiome sample collections by participant at-home	C	C

## 3.5 Participants

Primary participants will be patients with ALS (PALS) who are cared for by [name], or who contact our site inquiring about this study. 50 participants will be enrolled.

### 3.5.1 Inclusion Criteria

Each primary participant must meet all of the following criteria at screening and baseline (unless otherwise specified) to participate in the study:

1. Male or female, aged at least 18 years.
2. Sporadic or familial ALS diagnosed as possible, laboratory-supported probable, probable, or definite as defined by revised El Escorial criteria.
3. Patient is able to understand and express informed consent (in the opinion of the site investigator).
4. Patient has access to the Internet on a desktop computer, laptop, or tablet and has a working email address.
5. Patient or caregiver is willing and able to use a computer and enter data on a secure website.
6. Patient is able to read and write English.
7. Patient is expected to survive for the duration of the trial.
8. Women must not be pregnant (will have evidence of a negative pregnancy test obtained by local physician within past 7 days or be post-menopausal)
9. Women must not be able to become pregnant (e.g., post-menopausal, surgically sterile, or using adequate birth control methods) for the duration of the study and three months after study completion. Adequate contraception includes: abstinence, hormonal contraception (oral

contraception, implanted contraception, injected contraception or other hormonal contraception, for example patch or contraceptive ring), intrauterine device (IUD) in place for  $\geq 3$  months, barrier method in conjunction with spermicide, or another adequate method.

### **3.5.2     *Exclusion Criteria***

Primary Participants will be excluded for any of the following:

1. Patient is taking other experimental treatments for ALS (those that are part of an active research study).
2. Prior side effects from curcumin or turmeric containing products
3. Patient has a medical or psychiatric illness that could in the investigator's opinion interfere with the patient's ability to participate in this study.
4. Pregnant women or women currently breastfeeding.
5. Life expectancy shorter than the duration of the trial.
6. Taking an antiplatelet agent or anticoagulant (due to the theoretically increased risk of bleeding from curcumin products)

### **3.5.3     *Control Subjects***

In addition to the 50 primary participants described above, we will seek to enroll 50 healthy control participants. We will attempt to enroll one control subject from each enrolled primary participant's home, preferably a spouse or partner of similar age if possible. We plan to use this data to compare the control participants to the ALS participants at baseline, week 4 and month 6. We will not conduct further follow-up or collect additional samples with the control subjects. There are no specific inclusion or exclusion criteria for control subjects except living in the same household and free of any neurodegenerative disease. This is an observational only study for the control subjects that constitutes minimal risk for the control subjects.

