### 2.4 Curcumin

Curcumin is a chemical compound that is one of three curcuminoids found in the culinary spice turmeric. Curcumin has been studied in a wide variety of neurologic diseases and is purported to have many bioactive properties. It is widely available as a dietary supplement in multiple formulations from many commercial companies (8). The treatment Theracurmin utilized in this study is a formulation of curcumin (see section 3.2.1).

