### 2.6.1 *Alterations of the Fecal Microbiome*

As in Parkinson's disease (10), there is increasing recent evidence that abnormalities in the gut microbiome may play a role in ALS pathophysiology. In a mouse model of ALS, for example, dysbiosis and impaired intestinal tight junctions and permeability occur before symptom onset (11). Altering the mouse microbiome via germ-free conditions, broad spectrum antibiotics or introduction of specific bacteria (*Ruminococcus torques* or *Purabacteroides distasonis*) exacerbate the ALS phenotype (12). On the other hand, feeding the mice butyrate (13), a natural product of a healthy microbiome, or introduction of other specific bacteria (*Akkermansia muciniphilia*) (12) improve the ALS phenotype. Alteration of the intestinal microbiome in a worm model of ALS can also improve motor function (14). Three studies suggest that people with ALS have altered intestinal microbiomes compared to healthy controls (12, 15, 16); a fourth small study did not find such a difference (17).

The curcumin formulation used in Theracurmin has been shown to have the capability of altering the fecal microbiome in mice (18). If curcumin can lead to a more favorable fecal microbiome profile in patients with ALS, it may help to slow or reverse ALS progression.

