### **3.8 Capacity to Give Consent**

Only potential participants with appropriate capacity to provide informed consent will be offered a consent form.

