### **3.9 Risk Assessment**

Curcumin appears reasonably safe. Large meta-analyses indicate that participants have not been recorded to have had a major adverse event. Side effects are infrequent (<10%) mostly gastrointestinal such as nausea, constipation, diarrhea, indigestion, and abdominal pain. Some participants also experienced hot flashes (26-28). This side effect profile is fairly similar to that experienced by a small American pilot trial utilizing Theracurmin in patients with mild cognitive impairment (19).

Risk associated with participation in the Duke or PLM database include loss of confidentiality. Risks of logging into Internet for any website including PLM include inadvertently downloading malicious software such as viruses that could put personal information or computer integrity at risk. These risks are minimized by the properties of the PLM website (see below).

Participants will be provided with contact numbers for the research staff. All sites will have an appropriate staff member available 24 hours a day, 7 days a week in the event of an emergency. Participation in this research study is purely for research purposes, and is not intended to provide any direct benefit to the volunteers other than altruism (knowledge that they are helping investigators develop better treatments, and potentially helping other patients down the road). No at risk populations such as minors, prisoners, pregnant women, or cognitively impaired adults will be included in this study. Patients who elect not to participate will have standard of care options for their ALS including participation in [name] multi-disciplinary ALS clinic and the drug riluzole.

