#### **4.1.6 Microbiome Analyses**

We will compare saliva and stool microbiome samples between patients with ALS and healthy controls at every sampling point. We will compare the changes in the saliva and stool microbiome over time in patients with ALS on Theracurmin to the changes observed in untreated healthy controls. We will compare the enrollment saliva and stool microbiome across patients with different ALS origins (sporadic versus familial), onset regions (limb versus bulbar) and ALSFRS-R progression rates.

Raw, 16S microbiome sequencing data will undergo processing & strict quality control using the Qiime2 pipeline (31). Dada2 (32) will be used to infer and quantify amplicon sequence variants (ASVs). Taxonomy information will be assigned to the ASVs using the q2-feature-classifier (33) against the SILVA 132 database (34). Initial analyses of the data will focus on associations between the diversity of the microflora environment to ALS patients relative to the control samples as well as between the different forms of ALS. We will employ four different metrics for calculating within-sample diversity (alpha diversities: Faith's phylogenetic diversity, Shannon index, Pielou's evenness, and the total number of ASVs) and four different metrics for calculating between-sample diversities (beta diversities: Bray-Curtis dissimilarity, Jaccard dissimilarity, UniFrac, and weighted UniFrac). To identify associations between alpha diversity metrics and ALS, we will employ linear mixed-effects models with household as a random effect. Beta diversity indices will also be evaluated using mixed-effect modeling using the *vegan* package from the R statistical programming environment. The *PhyloSeq* (35) package will be employed to test for differential abundance of individual taxa between ALS patients and the control samples. In brief, raw ASV counts will be agglomerated in Family, Genus, and Species level data before being normalized by the 'poscounts' function from DESeq2 (36). Negative binomial linear models will then be used to identify differential abundance of microflora at the varied taxonomic ranks. Performing all analyses in a linear model framework will allow us to control for potential cofactors such as patient antibiotics usage, age, and gender. The false discovery rate will be used to control for multiple hypothesis testing.

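### The eligibility rules for household controls in 3.5.3 do not agree with 3.9, and the plan schedules no record of control supplement or antibiotic use, so the untreated status and the adjustment in 4.1.6 cannot be checked or applied

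*Combined protocol and SAP*

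**What the plan says.** Section 3.5.3 plans a household comparison group: "we will seek to enroll 50 healthy control participants", if possible one from each participant's home, "preferably a spouse or partner of similar age if possible". Its eligibility rule is: "There are no specific inclusion or exclusion criteria for control subjects except living in the same household and free of any neurodegenerative disease".

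Section 3.9 makes a statement about the study as a whole: "No at risk populations such as minors, prisoners, pregnant women, or cognitively impaired adults will be included in this study". Section 3.8 adds: "Only potential participants with appropriate capacity to provide informed consent will be offered a consent form".

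The criteria in 3.5.1 (including age 18 or over and the pregnancy rules) and 3.5.2 are each introduced as applying to primary participants.

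Section 4.1.6 compares saliva and stool microbiomes between patients and controls at every sampling point. It also compares patients' change over time on Theracurmin "to the changes observed in untreated healthy controls". It names antibiotic use, age and gender as covariates. Table 2 lists three activities for controls: consent, criteria review and sample collection. Table 1, for patients, includes concomitant medications.

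On curcumin in general, 2.4 says: "It is widely available as a dietary supplement in multiple formulations from many commercial companies".

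**The concern.** There are two separate problems.

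The first is a conflict of text. Section 3.5.3 does not leave the control criteria unstated; it says that only two exist. A coordinator doing the criteria review in Table 2 for a pregnant spouse would find that she meets both rules in 3.5.3 and is ruled out by 3.9.

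The second concerns what the analysis can support. The controls' change over time is the reference for change on Theracurmin. Curcumin can be bought freely, and under 3.2.2 a six-month supply of study product goes to the same home. If a control starts taking curcumin, that control's microbiome may move in the same direction as the patient's and the contrast narrows. If a control takes an antibiotic, the reference change shifts for an unrelated reason. The plan would record neither event, and an exposure that was never collected cannot be adjusted for later.

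**Working it through.** **Step 1: eligibility, side by side.**

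| Person in the household | 3.5.3 | 3.5.1 and 3.5.2 | 3.8 | 3.9 |
|---|---|---|---|---|
| Minor | meets both rules; similar age only preferred | primary participants only | may limit entry through capacity | not included |
| Pregnant adult | meets both rules | primary participants only | silent | not included |
| Curcumin user | meets both rules | primary participants only; prior side effects excluded, use itself not | silent | silent |
| Blood relative, familial ALS, no disease | meets both rules | familial ALS is eligible for patients | silent | silent |

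Only the first two rows conflict with 3.9. The last two bear on comparability.

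**Step 2: data needed against data scheduled for controls.**

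| Needed by 4.1.6 | Scheduled in Table 2 |
|---|---|
| untreated status through month 6 | no item |
| antibiotic use | no item |
| age, gender | no explicit item |

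In a model that includes both groups, a covariate has to be known in both. If antibiotic use is blank for controls, either the controls drop out of the adjusted model or blanks are read as no use and exposed controls are misclassified.

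**Step 3: possible size.** The plan has no sample-size calculation for the control comparison, so there is no stated figure to reproduce. What follows is an illustration under assumptions that are not in the documents.

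- Let a share f of controls start curcumin after baseline, with the same effect d as Theracurmin. The control mean change moves by f × d, so the contrast is d − f × d = d(1 − f).
- Take 50 against 50, two-sided 5%, independent groups, normal approximation. The standardized effect giving 80% power is d = (1.960 + 0.842) × √(2/50) = 0.56.
- Power at d(1 − f) is Φ(2.802(1 − f) − 1.960). The number per group that restores 80% power is 50/(1 − f)².

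| f | Contrast kept | Power | n per group for 80% |
|---|---|---|---|
| 0% | 100% | 80% | 50 |
| 5% | 95% | 76% | 56 |
| 10% | 90% | 71% | 62 |
| 20% | 80% | 61% | 79 |

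The calculation ignores household pairing and dropout. It does not describe a control who was already on a steady supplement at baseline: that person has no new exposure, so there is no reason for the change score to be diluted. Steady use could still affect the cross-sectional comparison of patients with controls, which this formula does not address.

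**Step 4: blood relatives.** The documents give no familial share. For each 5% of participants with familial ALS, at most 50 × 0.05 = 2.5 households could supply such a control, and fewer if the preferred spouse or partner takes part.

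**The case against.** The strongest reply is that the documents should be read together. Section 3.5.3 says that controls have no *specific* criteria, and 3.9 is a general rule that still covers them. Section 3.8 adds a capacity condition. On that reading no minor or pregnant woman enters. This stands in part: a reader might infer that the plan permits such enrolment, and the documents do not support that. They show two statements that do not agree. Limiting 3.9 to primary participants would resolve the matter equally well, since 3.5.3 calls the control part observational and minimal risk.

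A reader might also infer that a curcumin-using control contradicts the description of controls in 4.1.6. In context, untreated most naturally means not given study Theracurmin. The weakness is an assumption that nothing protects or checks, not a contradiction.

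Excluding current curcumin users from the controls is tempting, but 3.5.2 excludes patients only for prior side effects, not for use. A ban on one side would make the groups less alike at baseline.

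Excluding blood relatives is tempting as well, because 2.6.1 reports that in a mouse model "dysbiosis and impaired intestinal tight junctions and permeability occur before symptom onset". That one sentence is thin support. A relative free of disease contradicts neither 3.9 nor 4.1.6. Patients' familial status is needed for the planned subgroup analysis anyway, so these households can be set aside in a sensitivity analysis.

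Finally, 3.3.3 plans a within-patient comparison over time that needs no controls, so the secondary hypothesis on altering the microbiome does not rest on them alone. This is correct and limits the impact. None of these replies supplies the missing exposure record.

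**Conclusion.** Two points hold. Sections 3.5.3 and 3.9 are inconsistent on minors and pregnant women and must be reconciled. And 4.1.6 relies on an untreated reference group and an antibiotic adjustment for which the plan schedules no control data.

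The impact is confined to the secondary microbiome comparisons: change on Theracurmin against change in controls, and patients against controls. The primary ALSFRS-R comparison in 4.1.2 is unaffected.

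The size is unknown. The losses in the table depend on an assumed share of controls who start curcumin during the study and on an assumed effect equal to that of Theracurmin. They should not be read as the cost of failing to exclude people who already take curcumin. Nor would every problem be beyond repair: age and gender are planned covariates, and familial households can be identified. Supplement and antibiotic exposure is the part that is lost if it is not asked about during the study.

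**What to change.** 1. **Reconcile the text.** Either state control criteria in 3.5.3 that agree with 3.9, or limit the sentence in 3.9 expressly to primary participants. The choice is the sponsor's.
2. **Collect the exposure.** At enrollment, week 4 and month 6, ask each control about curcumin or turmeric use, including sharing of the study product, and about antibiotic use. At the two later samples the questions should cover the whole interval since the previous one, with start dates. Record age, gender and relationship to the patient. Add these items to Table 2.
3. **Add two sensitivity analyses to 4.1.6.** Run the change comparison with and without controls who began curcumin after baseline. Run the comparison of patients with controls with and without curcumin-using controls and blood relatives in familial-ALS households. The first selects on an event after baseline, so it should support the main analysis and not replace it.

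The cost is a short amendment, at most 50 × 3 = 150 brief sets of questions, and two extra model runs. No control need be turned away for curcumin use or kinship.
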